### Background

A local Practice-Based Research Network recently reported that one in five patients presenting to clinic for a methicillin-resistant *Staphylococcus aureus* (MRSA) skin infection experienced treatment failure within 90 days, at a mean cost of \$1,933 per patient. In a subgroup of patients with moderate-complicated skin abscesses, failure rates were 36%, despite receipt of guideline endorsed therapy. Several clinicians reported that household contacts (HCs) of these patients later came to clinic too, with similar skin infections. Other studies have demonstrated a 28% treatment failure rate after the incision and drainage of uncomplicated cutaneous abscesses. These findings demonstrate a clear need for interventions to promote healing and improve outcomes in patients with skin abscesses and reduce infections in their HCs. We believe Provodine can help satisfy this critical need.

### Study Design

We propose an open-label, randomized, pragmatic clinical trial for a pilot study to determine if Provodine can be used as an antiseptic and hand wash applied once daily to promote healing and improve outcomes in patients with skin abscesses and to reduce infections in their HCs. Patients will be randomized to Provodine or washing with soap and water. We have strategically selected our highest enrolling clinics from prior studies to start this investigation. If the results of this pilot study are promising, we will work with Microdermis to design and implement a follow-on statistically powered, clinical outcome study that will involve geographically distributed clinics and alternate sites around the US.

### Patients

#### *Study inclusion criteria*

1. Age 18 years or older
2. Skin abscess (i.e., pus)
3. Treatment requiring incision and drainage

*Study exclusion criteria:*

1. Unable or unwilling to provide informed consent
2. Homeless, incarcerated, or living in a group home
3. Abscess on the face or breast
4. Abscess requiring surgical drainage in the operating room or requiring admission to the hospital
5. Intravenous drug users
6. Previous enrollment in this study
7. Documented history of iodine sensitivity

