**Specific Aims**

1. Compare clinical cure rates in patients with cutaneous abscesses at 7 days
2. Compare rate of new lesion development within 30 days
3. Compare infection rates in HCs within 30 days

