**Methods**

Patients who meet criteria for the study will be enrolled by a convenience sample and randomized to a treatment group. Each patient will have a demographic data sheet completed by one of the study investigators or research associates. The data sheet will include contact information, age, gender, ethnicity, location of the abscess, measured length and width of palpable fluctuance and induration, measured length and width of surrounding cellulitis, presence or absence of fever, and previous medical history (including history of prior skin abscesses.) Assignment to a treatment group will be by blocked randomization.

All enrolled patients will be provided with an informed consent document and an overview of the study. Baseline measurements including size of abscess (measured by ruler of palpable fluctuance and induration) and maximal diameter of the largest area of cellulitis will be recorded. Providers will outline the area of palpable fluctuance with an Aspen skin marker and delineate the surrounding area of cellulitis with a dotted line to establish baseline surface area of wound. All patients will have standard care including incision and drainage and wound culture of the abscess cavity. All patients will receive local anesthesia and additional pain management will be left to the discretion of the treating provider. Providers will make a linear incision over the length of palpable fluctuance and induration. The provider will explore the wound cavity and break apart any loculations to allow for adequate drainage of purulent discharge. The provider will obtain wound cultures and irrigate with normal saline until clear irrigation fluid drains from cavity. Swabs will be sub-cultured on blood agar plates and grown overnight for bacterial identification and antibiotic susceptibility testing.

Patients randomized to Provodine will have the abscess cavity and surrounding skin gently painted with Provodine solution. The contents of one foil packet of Provodine will be applied with

a Q-tip to the walls and floor of the abscess cavity. The contents of a second foil packet will be applied to the surrounding skin within 5 cm around the incision.

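### Exclusion 6 lets an infected household contact enrol, possibly in the other arm, while the index patient is still in follow-up: a minor gap that is cheap to close

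*Combined protocol and SAP*

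**What the plan says.** All references are to the combined protocol and SAP.

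- **Patients, exclusion criteria.** The only criterion on re-entry is number 6, "Previous enrollment in this study". The only one on living situation is number 2, "Homeless, incarcerated, or living in a group home", which does not reach an ordinary shared home.
- **Patients, inclusion criteria.** A contact would need to meet "Age 18 years or older", have a skin abscess, and meet "Treatment requiring incision and drainage".
- **Methods.** "Patients who meet criteria for the study will be enrolled by a convenience sample and randomized to a treatment group". "Assignment to a treatment group will be by blocked randomization". No household cluster, same-arm rule, allocation ratio or block size is given. Contacts are assessed for infection but are not described as enrolled, so exclusion 6 does not apply to them.
- **Background.** Clinicians reported that "household contacts (HCs) of these patients later came to clinic too, with similar skin infections". No rate is given.
- **Specific Aims.** Aim 3 is "Compare infection rates in HCs within 30 days". Aim 2 is new lesions in the patient over the same 30 days.
- **Statistical Methods.** Cure, new lesions and infections are each compared yes/no by Fisher's exact test, two-sided at 5%. There is no adjustment for household. The sample size was not based on a power calculation.

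**The concern.** The event that Aim 3 counts can also make a person eligible for the trial. An adult contact with an abscess needing drainage, and none of the listed exclusions, is an outcome for the index patient and a candidate for randomisation. The Background makes this foreseeable. It does not say that those contacts attended the trial's own clinics, but that is a reasonable inference, since Study Design says the sites were chosen from the network's highest enrollers.

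If the contact is assigned to the other arm during the index patient's 30 days, three things follow.

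1. Other household members live with both regimens, so the second participant's Aim 3 result no longer reflects one arm only.
2. A third member who becomes newly infected while both follow-up windows are open could be counted once in each arm.
3. The two participants' outcomes are linked, and Fisher's exact test treats them as independent. This third problem arises even when both are in the same arm.

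**Working it through.** The plan states no figure on this point, so there is nothing to reproduce. The check has three parts.

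**Does any text close the gap?** No. Exclusion 6 concerns the person, exclusion 2 does not cover ordinary households, and Methods has no household rule for enrolment or assignment.

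**How many mixed households?** The input from the documents is about 130 enrolled (Timeline and Estimated Costs). The other inputs are assumptions:

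- h = share of index households with an infected contact during follow-up, 5-20%
- e = share of those contacts who are eligible and enrol, 10-50%
- 1:1 allocation, so a 0.5 chance of the opposite arm

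The 130 includes the contacts, so the number of index households K satisfies K × (1 + h × e) = 130. Contacts enrolled = K × h × e. Mixed households = half of that. Share of patients in a mixed household, m = 2 × mixed / 130. Chance of at least one = 1 − (1 − 0.5 × h × e)^K.

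| Case | h | e | K | Contacts enrolled | Mixed households | m | Chance of at least one |
|---|---|---|---|---|---|---|---|
| Low | 5% | 10% | 130/1.005 = 129.4 | 0.6 | 0.3 | 0.5% | 28% |
| Central | 10% | 25% | 130/1.025 = 126.8 | 3.2 | 1.6 | 2.4% | 80% |
| High | 20% | 50% | 130/1.10 = 118.2 | 11.8 | 5.9 | 9.1% | over 99% |

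**How much dilution?** Suppose both members of a mixed household take the mean of the two arm rates. The difference then becomes (p1 − p2) × (1 − m). The rates below are illustrative. Power is the normal approximation with 50 per arm (100 completers, split equally) at two-sided 5%.

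| Contrast | No mixing | Central, m = 2.4% | High, m = 9.1% |
|---|---|---|---|
| 20% vs 10%: difference | 10.0 points | 9.8 | 9.1 |
| 20% vs 10%: power | 28.6% | 27.5% | 24.4% |
| 28% vs 14%: difference | 14.0 points | 13.7 | 12.7 |
| 28% vs 14%: power | 40.3% | 38.7% | 34.4% |

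Exact power for Fisher's test with no mixing is lower, 19.5% and 32.2%, so the approximate values serve only to show the size of the change. Complete averaging within a mixed household is a severe assumption, so the dilution shown is more likely too large than too small for a given m.

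**The case against.** A reader might infer that both Aim 2 and Aim 3 are contaminated throughout the 30 days and pulled toward no difference in both participants. The documents do not support that.

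- **Index patient, Aim 3.** If the outcome is yes/no per index patient, that patient is already a yes when the contact enrols, and later mixing cannot change it. If infections were counted per contact, both records could be affected. The plan does not define the unit.
- **Aim 2.** A new lesion is an abscess, pustule, carbuncle or furuncle in the patient at least 5 cm from the initial wound. No passage says that such lesions arise by household transmission. The route is plausible, not documented.
- **Exposure.** Patients apply Provodine to themselves and contacts are not treated, so direct crossover would require sharing packets. The Provodine arm also washes hands with soap and water. Home treatment runs to the second recheck at 7-10 days or until the cavity closes. A contact who enrols later would normally find the index patient off study treatment.
- **Double scoring.** The visits and the 30-day call record new lesions, so the index patient's existing abscess is not an Aim 3 event for the second participant. Counting one infection in both arms mainly requires a newly infected third person in overlapping windows.
- **Proportion.** This is an unpowered pilot, and Methods enrols a convenience sample. Consent and the other exclusions would further reduce the number of contacts who enter.

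All of this stands, and it limits the harm. It does not close the gap. Nothing in the text prevents overlapping enrolment from one household, and the dependence between participants from one household remains whichever arms they are in. Pilot status is only a partial answer, because Study Design makes a larger trial depend on promising results and the criterion could be carried into it.

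**Conclusion.** The gap in eligibility is certain from the text; its consequence is small and uncertain. An infected adult contact can enter the opposite arm during the index patient's follow-up. The effect falls mainly on the second participant's Aim 3 record and on the independence assumption.

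Under the assumed rates, about 0.6-12 contacts enrol and about 0.3-6 households are mixed, with about 1.6 in the central case. The illustrative 10-point difference loses about 0.2 points in the central case and 0.9 at the upper end. These sizes rest wholly on the assumed 5-20% infection share, 10-50% enrolment share and 1:1 allocation. Severity: minor, a cheap improvement.

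**What to change.** Keep exclusion 6 as "Previous enrollment in this study" and add to it: *or living in the same household as a participant who has not completed the 30-day follow-up*. Ask this at screening. Continue to count the contact's infection as an Aim 3 event for the index patient, so that the exclusion removes no outcome data.

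Overlapping mixed-arm households from this route then fall to zero by design, as do third-member infections counted in both arms and dependence between household members followed at the same time. Limiting the rule to open follow-up keeps household members who present later in the roughly one-year accrual eligible.

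The cost is one line, one question, and about 0.6-12 of 130 otherwise eligible patients under the assumptions, about 3 in the central case. Assigning the contact to the index patient's arm would lose no one, but it would leave within-household correlation for the analysis to handle. Neither option settles whether Aim 3 is scored per patient or per contact, which the plan should state separately.

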**Hypothesis**

We believe patients who use Provodine as an antiseptic and hand wash once daily for at least 7 days will have better healing, better health outcomes, fewer treatment failures and fewer infections themselves and among their household contacts (HCs) than those who do not use Provodine.

**Specific Aims**

1. Compare clinical cure rates in patients with cutaneous abscesses at 7 days
2. Compare rate of new lesion development within 30 days
3. Compare infection rates in HCs within 30 days

**Methods**

Patients who meet criteria for the study will be enrolled by a convenience sample and randomized to a treatment group. Each patient will have a demographic data sheet completed by one of the study investigators or research associates. The data sheet will include contact information, age, gender, ethnicity, location of the abscess, measured length and width of palpable fluctuance and induration, measured length and width of surrounding cellulitis, presence or absence of fever, and previous medical history (including history of prior skin abscesses.) Assignment to a treatment group will be by blocked randomization.

All enrolled patients will be provided with an informed consent document and an overview of the study. Baseline measurements including size of abscess (measured by ruler of palpable fluctuance and induration) and maximal diameter of the largest area of cellulitis will be recorded. Providers will outline the area of palpable fluctuance with an Aspen skin marker and delineate the surrounding area of cellulitis with a dotted line to establish baseline surface area of wound. All patients will have standard care including incision and drainage and wound culture of the abscess cavity. All patients will receive local anesthesia and additional pain management will be left to the discretion of the treating provider. Providers will make a linear incision over the length of palpable fluctuance and induration. The provider will explore the wound cavity and break apart any loculations to allow for adequate drainage of purulent discharge. The provider will obtain wound cultures and irrigate with normal saline until clear irrigation fluid drains from cavity. Swabs will be sub-cultured on blood agar plates and grown overnight for bacterial identification and antibiotic susceptibility testing.

Patients randomized to Provodine will have the abscess cavity and surrounding skin gently painted with Provodine solution. The contents of one foil packet of Provodine will be applied with

a Q-tip to the walls and floor of the abscess cavity. The contents of a second foil packet will be applied to the surrounding skin within 5 cm around the incision.

The abscess cavity of both groups will be gently packed with  $\frac{1}{4}$  inch plain gauze strips and the wound will be covered with 4x4 gauze and secured with tape. Patients will be instructed to leave the wound packing in place and change the outer dressing once a day until they return at 48-72 hours for their first wound recheck.

Several studies have shown that there is no clinical benefit to antibiotics in the routine management of uncomplicated abscesses. Patients with uncomplicated abscesses (defined as palpable abscess < 5 cm in a healthy patient with no history of diabetes, HIV, IVDA or immunocompromised state who has no systemic signs of infection) will not be treated with antibiotics. Patients who do not meet these criteria will be treated with antibiotics at the discretion of the provider.

A study investigator will evaluate the patient in the emergency department or clinic within 48- 72 hours for the initial follow up visit and the packing will be removed. Patients randomized to Provodine will have the contents of the foil packet reapplied to the walls of the abscess cavity and surrounding skin. Data that will be collected on initial recheck include presence or absence of fever, purulent drainage, erythema, and pain, as well as presence of new skin lesions. A new lesion is defined as a new abscess, pustule, carbuncle, or furuncle at least 5 cm away from the initial wound. Lesions within 5 cm of initial wound will be considered failures of the initial abscess treatment.

Study investigators will also record compliance with intervention and side effects. Compliance will be assessed by measuring the amount of opened foil packets and by patient report. The cure rate, as measured by the absence of fever, pain, erythema and purulent discharge, will be recorded as well as the overall assessment by the provider if wound is improving, unchanged, or clinically worsened.

Wound management will be left up to the discretion of the treating provider, but further incision and drainage, wound repacking and antibiotic use will be reserved for patients determined to be not clinically improving or getting worse and will be considered a treatment failure. Outcomes including clinical cure, rate of new lesion development in patients and HCs, and therapeutic changes to clinical management will be recorded.

After the packing is removed, all patients will be instructed to cleanse the abscess at home by soaking in water once a day and gently patting the wound dry. Patients will follow specific instructions for wound management once a day after washing.

After cleansing and drying the abscess, the patients randomized to the Provodine arm will wash their hands with soap and water, pat dry, and apply the contents of one foil packet of Provodine to dorsum and palmar aspects of hands and fingers and rub hands and fingers together for one minute to ensure all skin distal to the wrist is covered. They will then apply the contents of a second foil packet to the walls and floor of the abscess cavity using a Q tip applicator. The patient will then apply a third foil packet of Provodine to the skin surrounding the abscess within 5 cm diameter of the wound using a separate Q tip. After applying Provodine to the abscess and surrounding skin, they will be then gently rinse their hands with water, pat hands dry, and cover the wound with a 4x4 gauze dressing.

The patient will also be instructed to keep a Ziploc bag of empty Provodine foil packets to assess compliance at follow up visits.

[figure not shown]
Patients randomized to standard care will cover wound with 4x4 gauze dressing and wash hands with soap and water for one minute. Patients will be instructed to continue to perform once daily cleansing/treatments until they are seen for their second wound recheck or until wound cavity has closed.

The patient will return for a 2nd visit between 7 and 10 days for a second wound recheck. Data that will be collected will be the same as on initial recheck including the presence or absence of fever, purulent drainage, erythema, and pain, as well as presence of new skin abscesses in the patient or HCs.

Study investigators will also record compliance with intervention and side effects. Compliance will be assessed by measuring the amount of opened foil packets and by patient report. The cure rate, as measured by the absence of fever, pain, erythema and purulent discharge, will be recorded. Wound management will again be left up to the discretion of the treating provider, but further incision and drainage, wound repacking and antibiotic use will be encouraged only for patients determined to be not clinically improving or getting worse and will again be considered a treatment failure. Outcomes including clinical cure, reinfection, rate of new lesion development, and therapeutic changes to clinical management will be recorded.

Patients will be called at home at 30 days to assess for treatment failures requiring additional intervention and new lesion development in patients and their HCs.

The figure below depicts the timing of assessments for patients (Pts) and household contacts (HCs). Outcomes include rate of clinical cure rate of initial abscess and rate of new lesion development. Therapeutic changes (e.g., addition of new antibiotics or additional incision and drainage), or unplanned health care encounters for the skin infection (e.g., urgent care visits, emergent care visits, or hospital admissions) will be considered treatment failures. Fisher's exact test will be used to compare outcomes between groups.

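### Several clinics enrol, but the plan does not say that blocks run within clinic and tests only with pooled Fisher's exact tests: avoidable chance imbalance and some lost precision, not bias

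*Combined protocol and SAP*

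**What the plan says.** All references are to the combined protocol and SAP.

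- **Sites.** Study Design speaks of clinics in the plural: "We have strategically selected our highest enrolling clinics from prior studies to start this investigation". Their number is not given.
- **Allocation.** Methods gives one sentence: "Assignment to a treatment group will be by blocked randomization". No ratio, block size or stratification factor follows. Clinic is not among the items listed for the data sheet.
- **Discretion.** Methods states "Wound management will be left up to the discretion of the treating provider", and for abscesses outside the uncomplicated definition, "Patients who do not meet these criteria will be treated with antibiotics at the discretion of the provider". Further drainage, repacking or antibiotics are for patients "determined to be not clinically improving or getting worse and will be considered a treatment failure". The same rule, worded a little more loosely, applies at the second recheck.
- **Analysis.** Methods says that Fisher's "exact test will be used to compare outcomes between groups". Statistical Methods repeats this for cure, new lesions and infections, two-sided at 5%. Neither section mentions clinic.
- **Size.** Timeline and Estimated Costs plans for 100 patients completing the second recheck, from about 130 enrolled. Statistical Methods says that no power calculation lies behind this.

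**The concern.** Clinics may differ in case mix, in antibiotic use for complicated abscesses and in how readily they re-treat. Because re-treatment is itself a failure event, a local threshold feeds directly into that outcome. Cure is reached less directly, through the rating of pain and erythema in an open-label trial.

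Both possible readings of the allocation sentence leave something undone. If one list serves all clinics, the arms are balanced overall but can be uneven inside a clinic. If each clinic has its own list, the pooled Fisher test ignores the strata within which patients were randomised, and the precision that stratifying could give is not used.

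At stake are the precision of each contrast in a small trial, and how far a single realised difference can be told apart from a chance difference in clinic mix. The pilot is also meant to inform a larger trial over more sites, so how much outcomes vary between clinics is worth knowing.

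**Working it through.** The plan contains no power figure to reproduce. The inputs it gives are 100 completers, about 130 enrolled (non-completion 30/130 = 23.1%), two-sided 5%, and a 28% failure rate after drainage of uncomplicated abscesses (Background), used here as an illustrative control rate. Assumed: 1:1 allocation, blocks of 4, clinics of equal expected size, 2 to 6 clinics, and the clinic variation shown below.

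**1. Imbalance within clinics (simulation).** 130 patients are allocated and a random 100 complete. The event is that at least one clinic has 60% or more of its completers in one arm.

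| Clinics | One central list | Blocks within clinic |
|---|---|---|
| 2 | about 15% | about 1% |
| 4 | about 73% | about 25% |
| 6 | about 96% | about 65% |

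At randomisation, blocks of 4 within clinic hold the difference to 2 patients per clinic. Dropout then undoes part of that, which is why the right-hand column is not near zero.

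**2. Variance attributable to clinic.** The share is the between-clinic variance divided by p(1 − p), where p is the mean cure rate.

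- Clinic cure rates 0.55, 0.65, 0.75, 0.85: p = 0.70, share = 0.0125/0.21 = 6.0%. The standard error falls by 1 − √(1 − 0.060) = 3%.
- Clinic cure rates 0.45, 0.60, 0.75, 0.90: p = 0.675, share = 0.0281/0.2194 = 12.8%. The standard error falls by 1 − √(1 − 0.128) = 7%, equivalent to 1/(1 − 0.128) = 1.15 times the patients.

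**3. Shift in the pooled difference from chance clinic imbalance.** With 50 per arm and the first set of rates, the standard deviation of the shift is about √(4 × 0.0125/100) = 2.2 percentage points, with mean zero. The full standard error is √(4 × 0.21/100) = 9.2 points.

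**4. Type I error and power (simulation).** 100 patients, 4 clinics, one central list, normal clinic effects on the logit scale, 4,000 runs per setting. The Mantel-Haenszel test is stratified by clinic, without continuity correction. The 14% fixes the odds ratio, which is held constant as the clinic SD changes.

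| Failure rates | Clinic SD | Pooled Fisher | Mantel-Haenszel |
|---|---|---|---|
| 28% v 28% | 0 | 3.3% | 5.3% |
| 28% v 28% | 0.5 | 3.4% | 5.4% |
| 28% v 28% | 1.0 | 3.0% | 4.7% |
| 28% v 14% | 0 | 31% | 38% |
| 28% v 14% | 0.5 | 32% | 41% |
| 28% v 14% | 1.0 | 27% | 37% |

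The Monte Carlo standard error of a power figure is about √(0.3 × 0.7/4000) = 0.7 points. Taking both allocation schemes and repeated simulation together, the ranges are about 28–34% for Fisher and 38–42% for Mantel-Haenszel.

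The gap is 38 − 31 = 7 points when clinics do not differ at all, and 37 − 27 = 10 points at SD 1.0. So about 7 of the 10 points come from Fisher's conservatism and about 3 from clinic variation.

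**The case against.** The case for leaving the plan alone has real force.

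- **Much of the care is standardised.** Methods prescribes the incision, loculation, irrigation and packing steps, and withholds antibiotics for uncomplicated abscesses. At the first recheck, "A study investigator will evaluate the patient in the emergency department or clinic". A reader might infer that everything affecting outcome lies with the local provider. The text does not support that: discretion bears mainly on treatment failure, while cure is defined by four signs.
- **Silence is not exclusion.** A reader might infer that the randomisation ignored clinic. The plan says only that it is blocked, and the blocks may run per clinic. On allocation the point is that this is unstated. On the analysis, the pooled test is explicit.
- **The harm is limited.** Uneven arms within a clinic matter only through the pooled difference, and the typical shift (2.2 points) is small beside the standard error (9.2 points).
- **It is a pilot.** The plan disclaims a power calculation and defers the powered comparison to a later trial.
- **The remedy has a price.** Small blocks within clinic make the next assignment easier to guess in an open-label study.

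All of this stands, and it limits the size of the point. It does not remove it: the plan still does formal 5% testing on these outcomes, and a more precise comparison costs almost nothing.

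**Conclusion.** The point holds as a modest improvement. The plan leaves open whether blocks run within clinic, and its pooled Fisher tests discard clinic information.

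A reader might infer that clinic differences bias the treatment comparison or make the test invalid. They do not: randomisation leaves no systematic bias, and Fisher's type I error stays at about 3% across the clinic effects tried. A reader might also expect blocking within clinic to abolish imbalance. With 30 of 130 patients not completing, it reduces it, from about 73% to 25% with 4 clinics and from 96% to 65% with 6.

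The precision gain from clinic itself is about 6% of the variance under moderate assumed variation and about 13% under wide variation. Most of the power difference between the two tests comes from Fisher's conservatism. All of these sizes rest on assumed numbers of clinics, block size, random dropout and clinic rates. With only 2 clinics the imbalance risk is small on either scheme.

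**What to change.** In Methods, state the allocation ratio, use permuted blocks of varying size within each clinic, and add clinic to the data sheet.

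In Statistical Methods, compare cure, new lesions and treatment failure with a clinic-stratified Mantel-Haenszel risk difference and test, or an exact stratified test. Add a pre-stated rule for pooling very small clinics. Keep the pooled Fisher test as supportive.

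The cost is one allocation list per clinic and a few lines of SAP text, with no extra patients. The downside is slightly easier guessing of assignments in an open-label trial, which varying the block sizes limits. If enrolment has begun, the stratified analysis can still be adopted on its own, provided each patient's clinic is recorded.

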## **Timeline and Estimated Costs**

We will continue enrollment until 100 patients complete their second wound care follow up and estimate this will take approximately 1 year. We anticipate enrollment of about 130 patients. Microdermis will provide Provodine at no cost to the patients.

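### Neither the randomisation nor the Fisher tests use complicated/uncomplicated status, a baseline factor that gates antibiotics; a stratified list and test would be a cheap, modest gain.

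*Combined protocol and SAP*

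**What the plan says.** On allocation, the Methods section states that "Assignment to a treatment group will be by blocked randomization". It gives no stratification factor, block size or ratio. The Study Design section names the two arms: "Patients will be randomized to Provodine or washing with soap and water".

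On antibiotics, the Methods section uses a status fixed by baseline findings. Uncomplicated abscesses are "defined as palpable abscess < 5 cm in a healthy patient with no history of diabetes, HIV, IVDA or immunocompromised state", with the further condition of no systemic signs of infection. These patients "will not be treated with antibiotics". For everyone else, "Patients who do not meet these criteria will be treated with antibiotics at the discretion of the provider".

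On analysis, the end of the Methods section and the Statistical Methods section both name Fisher's exact test for the group comparisons. No stratified, adjusted or subgroup analysis by complicated status is planned. Statistical Methods does not name that status, or antibiotic use at baseline, among the items to be tabulated by arm.

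On size, the Timeline section says "We will continue enrollment until 100 patients complete their second wound care follow up" and "We anticipate enrollment of about 130 patients". Statistical Methods says that the number was not derived from a power calculation.

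**The concern.** Complicated status is known when the patient is enrolled, and it decides who may receive an active co-treatment. It is plausibly prognostic for cure, which is defined as absence of fever, pain, erythema and purulent discharge: the complicated group includes patients with systemic signs and those with larger abscesses. It also bears on how failure is counted. Adding antibiotics later is a treatment failure, and patients who already had antibiotics at baseline do not reach that event in the same way as patients who had none.

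The Background points the same way: "In a subgroup of patients with moderate-complicated skin abscesses, failure rates were 36" per cent, against 28% reported elsewhere for uncomplicated abscesses after incision and drainage.

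The pilot is meant to inform whether a powered follow-on study goes ahead, and that judgement will rest on one realised allocation. If one arm happened to hold noticeably more complicated patients, a difference in cure would be open to the objection that it reflects case mix or antibiotics, and the planned analysis has no answer to it.

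**Working it through.** The plan states no probability of imbalance and no power, so there is no figure of that kind to reproduce. Its two sample sizes imply 1 − 100/130 = 23% non-completion, a rate that it does not state.

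**Inputs from the documents.** 100 completers and about 130 enrolled (Timeline); failure rates of 36% and 28% (Background); two-sided 5% Fisher tests (Statistical Methods).

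**Assumptions.** 1:1 allocation, hence 50 or 65 per arm; a share p of complicated patients between 10% and 50%, because the documents give none; a 10-point gap as the threshold of interest.

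**Step 1: chance of a gap.** Let X and Y be independent Binomial(n, p) counts of complicated patients in the two arms. The exact chance is P(|X − Y| ≥ k). A 10-point gap means k = 5 at n = 50, and k = 7 at n = 65 (0.10 × 65 = 6.5, rounded up). A 20-point gap means k = 10 at n = 50.

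| p | ≥10 points, n = 50 | ≥10 points, n = 65 | ≥20 points, n = 50 |
|---|---|---|---|
| 10% | 0.13 | 0.06 | 0.002 |
| 20% | 0.26 | 0.15 | 0.02 |
| 30% | 0.33 | 0.21 | 0.04 |
| 40% | 0.36 | 0.24 | 0.05 |
| 50% | 0.37 | 0.25 | 0.06 |

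The counts are coarse. Asking for 6 patients rather than 5 at n = 50 lowers that column to 0.07–0.27. Holding the total number of complicated patients fixed (hypergeometric) gives 0.09–0.36 at n = 50 and 0.08–0.29 at n = 65 over the same range of p.

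**Step 2: what a gap does to the result.** Shift in the arm difference = gap × (failure rate in complicated − failure rate in uncomplicated).

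- Background rates, 10-point gap: 0.10 × (36 − 28) = 0.8 points. 20-point gap: 0.20 × 8 = 1.6 points.
- Assumed 36% vs 10%, 10-point gap: 0.10 × 26 = 2.6 points. 20-point gap: 0.20 × 26 = 5.2 points.
- For scale, the standard error of the arm difference at 28% failure and 50 per arm is √(2 × 0.28 × 0.72 / 50) = 0.090, about 9 points.

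**Step 3: is Fisher's test still valid?** Type I error was enumerated exactly at 50 per arm, with 36% or 50% complicated and failure of 36% in complicated against 28%, 20% or 10% in uncomplicated patients. Unconditionally it is about 0.03 throughout. Given a 10-point gap it is 0.028–0.031. Given a 20-point gap it is 0.032–0.039 for 36% vs 28% or 20%, and about 0.053 only for 36% vs 10%.

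**Step 4: what stratified lists would do.** With one central list per status and permuted blocks of 4 (assumed), the arms can differ by at most 2 patients per stratum at randomisation: 2/50 = 4 points or 2/65 ≈ 3 points. A 10-point gap at randomisation is then ruled out.

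**Step 5: gain from a stratified test.** In simulation with 40% complicated, 50 per arm and an odds ratio of about 3 (all assumed), an exact stratified test gained about 2–7 points of power over Fisher's test, with type I error still below 5%.

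**The case against.** Blocked randomisation without stratification is a legitimate design, and this is an unpowered pilot. Chance imbalance does not bias the estimate over repeated randomisations, and Fisher's test holds its level. The 36% and 28% come from different studies. The first is a subgroup of an MRSA clinic cohort followed to 90 days; the second has no stated time window. Neither is this trial's early cure endpoint, so they do not establish how prognostic the status is here. Taken at face value, they make a 10-point gap nearly harmless. Abscess size, fever and medical history are recorded at baseline, so status can largely be reconstructed and adjusted for afterwards. Stratified lists would not balance the provider's open-label choice of antibiotics among complicated patients, and dropout could reopen a gap among completers.

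All of this stands, and it sets the size of the point. It does not remove it: the plan provides neither the reconstruction nor the adjusted analysis nor the table, and each is cheap.

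A reader might infer a one-in-three chance of a material imbalance. That needs 50 completers per arm, 30–50% complicated and a 10-point threshold. The documents give neither that share nor that threshold, and on their own rates such a gap is not shown to be material. A reader might also infer that the Fisher comparison is invalid or biased; step 3 of the working does not support that.

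**Conclusion.** The point holds as a minor design improvement. Allocation and analysis both leave out a baseline factor that gates antibiotic use and is plausibly prognostic for cure. The cost is some precision and a result that is harder to interpret if the arms differ by chance.

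The chance of a gap of 10 points or more is about 13–37% at 50 per arm and 6–25% at 65 per arm. This rests on 1:1 allocation and 10–50% complicated patients, both assumed. Such a gap moves the arm difference by under 1 point on the Background rates, and by about 2.6 points under the assumed wider contrast, against a standard error of about 9 points. Nothing here puts the pilot's validity in doubt.

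**What to change.** - **Before enrolment starts:** record complicated/uncomplicated status, as the Methods section defines it, as an explicit baseline item before the allocation is opened. Allocate from one blocked list per status.
- **Statistical Methods:** compare cure with an exact stratified (Mantel-Haenszel-type) test on that status in place of the plain Fisher test.
- **If enrolment has begun:** keep the existing list and make only the analysis change, deriving status from the recorded baseline data.
- **In either case:** tabulate status and baseline antibiotic use by arm, for patients randomised and for completers, because stratification balances neither the provider's discretion nor later dropout.

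The cost is one extra list and a line or two in Statistical Methods. The downside is that status must be settled before allocation, for a modest expected gain (about 2–7 points of power in the assumed scenarios).
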